14.4 Investigator's responsibilities and processing timelines

14.4.1 Materiovigilance

All incidents will be reported to LP vigilance manager according to MDR, MEDDEV 2.12 rev 8 modalities, national requirements, ISO 14155:2020 and Lallemand Pharma procedures which are described in the safety management plan. This document will be signed by the Principal Investigators of all participating sites, representants of the Clinical Research Organization (CRO), CRA in charge of the monitoring and the Vigilant Manager, before the study start.

As soon as the investigator will be informed of the event, he/she will complete a Primary Notification Form template (PNF, appendix C) and send it to the sponsor ([contact] and/or [contact] (as back-up method) and to the Vigilance manager [name] ([contact]), to the CRO ([contact] and/or [contact]), to the EU representative [name] ([contact]), and to the local CRAs ([contact] and [name]) with any relevant supportive documentation within the same day (<24h) for serious (risk) incident and within two calendar days (<48h) for non-serious incidents.

14.4.2 Vigilance reporting according to Article 80 of the MDR

Although not expected in this investigation with no invasive procedure, the following events are considered reportable events in accordance with MDR Art. 80(2):

- a) Any serious adverse event that has a causal relationship with the investigation procedure or where such causal relationship is reasonably possible.
- b) Any new findings in relation to any event referred to in point a)

For the purpose of harmonizing reports, each SAE will be classified according to four different levels of causality as per definitions of the MDCG 2020-10/1 rev 1 specified in the safety management plan:

- 1. Not related
- 2. Possible
- 3. Probable
- 4. Causal relationship

Only causality level 1 (i.e. "not related") is excluded from reporting.

Any serious adverse event that has a causal relationship with an investigational procedure will be reported by the investigator to the sponsor ([contact] and/or [contact] (as back-up method) and to the Vigilance manager [name] ([contact]), to the CRO ([contact] and/or [contact]), to the EU representative [name] ([contact]), and to the local CRA ([contact]) and [contact] immediately, but not later than 3 calendar days after investigation site study personnel's awareness of the event. To this end, the investigator will complete the "SAE form" (appendix D).

14.5 Sponsor responsibilities and processing timelines

14.5.1 Materiovigilance

The vigilance manager of Lallemand Pharma is responsible for the reporting to the Bulgarian Competent Authority.

Briefly, for serious incidents or risk of serious incident, the vigilance manager will complete a Manufacturer Incident Report. The result of the investigation conducted by the sponsor may lead to the implementation of a safety corrective action and completion of a Field Safety Corrective Action (FSCA) and of a Field Safety Notice. These documents will be transmitted to the Bulgarian Competent Authority and to the Ethics Committee ([contact]) in accordance with the timelines provided in the table below:

Serious Public Health Threat	Report immediately but not more than 2 days
Death or UNANTICIPATED Serious Deterioration in status of health	Report immediately but not more than 10 days using electronic Manufacturer Incident Report Form (+ paper version for the EC)
Others (could have led to death or serious deterioration in health)	Report immediately but not more than 15 days using electronic Manufacturer Incident Report Form (+ paper version for the EC)
Every FSCA	Immediately before the measure is implemented except in case of emergency, when the vigilance manager of the sponsor has to immediately take a safety corrective action, using the electronic FSCA form

Increase rate of non-serious incidents will be reported to the Bulgarian Competent Authority in Trend reports as per regulation requirements.

Responsibilities of sponsor are detailed in the Safety Management Plan.

14.5.2 Vigilance according to Article 80

Any serious adverse event that has a causal relationship with an additional procedure or a causal relationship reasonably possible, will be reported by the sponsor to the Bulgarian CA and the Ethics Committee as follows:

Any serious adverse event that has a causal	Immediately, but not later than 2 calendar days
relationship with the additional procedure or	after awareness by sponsor of a new reportable
a causal relationship reasonably possible,	event or of new information in relation with an
will be reported to the Bulgarian CA by the	already reported event. The excel file provided by
sponsor as follows: Imminent risk of death,	the MDCG 2020-10/2 rev1 is to be used.
serious injury, or serious illness and that	
requires prompt remedial action for	
patients/subjects or a new finding to it	
Other reportable events or a new	Immediately, but not later than 7 calendar days
finding/update to it	following the date of awareness by the sponsor of
	the new reportable event or of new information in
	relation with an already reported event. The excel
	file provided by the MDCG 2020-10/2 rev 1 is to be
	used.

15. Suspension, or premature termination of the Clinical Investigation

Lallemand Pharma AG may suspend or prematurely terminate the clinical investigation. The reasons shall be documented. Reasons for suspension or premature termination at an investigation site may include occurrences where monitoring or auditing identifies serious or repeated deviations on the part of an investigator. Lallemand Pharma AG will notify the Regulatory Authority as appropriate and ensure that the EC is notified of any suspension or early termination of the clinical investigation.

If suspicion of an unacceptable risk to subjects arises during the clinical investigation, or when so instructed by the EC or Regulatory Authority, Lallemand Pharma AG will suspend the clinical investigation while the risk is assessed. The sponsor will terminate the clinical investigation if an unacceptable risk is confirmed. The decision to maintain or to unblind the study will be taken in consultation with the Regulatory Authority. Should the risk not be confirmed Lallemand Pharma AG will, in accordance with regulations, provide relevant persons with justification and data supporting the decision to resume the clinical investigation.

EC or Regulatory Authority may suspend or prematurely terminate participation of one site or of all the participating sites.

The patients will receive all treatments needed in case of complication or safety issues. In this case, the patient will be followed until the end of the issue.

16. Publication policy

The information and data collected during the conduct of this clinical study are considered confidential and are used by the sponsor in connection with the development of the study treatment. This information will be disclosed by the sponsor depending on current regulations.

To allow use of the information derived from this clinical study and to ensure compliance with current regulations, the investigator must provide the sponsor with complete test results and all data collected during the study.

Only the sponsor may make study information available to physicians and to Regulatory Agencies, except as required by current regulations.

Appendix A: IFU

HEALSEA®BABYKIDS

[figure not shown]

INDICATION	UNDESIRABLE EFFECTS.		
Healsea® babykids is a nasal spray indicated in	In case of undesirable effects, contact your doctor.		
children above 2 years to clean and moisten the nose			
during colds and rhinitis			
COMPOSITION	STORAGE AND WASTE RECOMMENDATION		
Isotonic saline solution (salinity 0.9%),	Store at room temperature and not above 30°C.		
Symbiofilm®.	See the expiry date on the box or the bottle.		
	Ask your pharmacist to throw out the bottle after use.		
	These measures contribute to protect the		
	environment.		
DIRECTION OF USE	TECHNOLOGY		
Healsea® BABYKIDS shall be administered in children	The spray pump APF (Advanced Preservative Free)		
with the help of an adult.	uses a technology that permits to dispense a		
One-two sprays twice a day in each nostril for 10 days	preservative free solution.		
or as recommended by your doctor or pharmacist.			
PRECAUTION OF USE	HOW TO USE HEALSEA® BABYKIDS?		
- Keep out of reach of children.	1. Place the nozzle smoothly into the nostril while		
-If symptoms persist more than 10 days, ask for	keeping head straight.		
advices to your doctor or pharmacist.	2. Once the nozzle is placed, press on the nozzle in		
-The bottle shall be used by only one person for	each nostril. Let flow the excess of solution and		
hygiene reason and to avoid the transmission of	wipe.		
pathogenic agents that could be in contact with the	3. Clean the nozzle with tissue, soapy water, rinse		
nozzle.	and dry after every use.		
CONTRAINDICATION			
Do not use in children and adolescents under 2			
years.			
Do not use in case of hypersensitivity or allergy to one			
or several components.			

Healsea® BABYKIDS is a nasal spray containing isotonic saline solution mixed with an innovative extract, Symbiofilm®, isolated from the marine biosphere.

Healsea® BABYKIDS is a natural care preservative free allowing to clean and moisten the nasal mucosa. Symbiofilm® is a marine postbiotic, which contains exopolymeric substances, that enhances mechanically the cleansing efficiency of isotonic water.

Symbiofilm® reduces the development of biofilm from respiratory pathogenic microorganisms by mechanical action as well as the mucosal adhesion and helps reducing the spreading of viruses in-vitro. Healsea® BABYKIDS is the ideal solution for children who suffer from colds or rhinitis by cleaning the nasal cavity and eliminating allergens and infectious agents.

Date: Switzerland

Learn more about biofilms by flashing this QR code!

Publication 2021/12/10_R1

EC REP

ASPE CONSEIL [name]

Version 1.1 -2023.02.02 Study Number: LPH-2202

Page **56** of **64**

PLACEBO

INDICATION	UNDESIRABLE EFFECTS.
The Medical Device is a nasal spray indicated in	In case of undesirable effects, contact your doctor.
children above 2 years to clean and moisten the nose	
during colds and rhinitis	
COMPOSITION	STORAGE AND WASTE RECOMMENDATION
Isotonic saline solution (salinity 0.9%)	Store at room temperature and not above 30°C.
	See the expiry date on the box or the bottle.
	Ask your pharmacist to throw out the bottle after use.
	These measures contribute to protect the
	environment.
DIRECTION OF USE	TECHNOLOGY
The Placebo shall be administered in children	The spray pump APF (Advanced Preservative Free)
with the help of an adult.	uses a technology that permits to dispense a
One-two sprays twice a day in each nostril for 10 days	preservative free solution.
or as recommended by your doctor or pharmacist.	
PRECAUTION OF USE	HOW TO USE THE PLACEBO?
- Keep out of reach of children.	Place the nozzle smoothly into the nostril while
-If symptoms persist more than 10 days, ask for	keeping head straight.
advices to your doctor or pharmacist.	2. Once the nozzle is placed, press on the nozzle in
-The bottle shall be used by only one person for	each nostril. Let flow the excess of solution and
hygiene reason and to avoid the transmission of	wipe.
pathogenic agents that could be in contact with the	3. Clean the nozzle with tissue, soapy water, rinse
nozzle.	and dry after every use.
CONTRAINDICATION	
Do not use in children and adolescents under 2	
years.	
Do not use in case of hypersensitivity or allergy to one	
or several components.	

Lallemand Pharma AG [name]

EC REP

ASPE CONSEIL [name]

Page **57** of **64**

Version 1.1 –2023.02.02

Study Number: LPH-2202

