3.7.3 Primary and secondary packaging and labelling

The primary packaging is a white vial (Figure 2)

Figure 2: primary packaging

The secondary packaging is a white cardboard box.

A white label is sticked on the primary packaging with the following mentions:

	LPH-2202- Study BASICC	
Saline isotonic solution 0,9% and Symbiofilm 0.04% (Healsea® Babykids) or isotonic nasal saline solution (Placebo). Nasal spray, nasal route, vial 20 ml Posology: two sprays, twice a day in each nostril during a treatment period of 7 to 10 days		
Batch number:	Investigator:	
Treatment:	Patient:	
Expiry Date (mm/yyyy):/	Site:	
	For Clinical Investigation use only	

A white label is sticked on the secondary packaging with the following mentions:

	LPH-2202- Study BASICC
Saline isotonic solution 0,9% and Symbiofilm or isotonic nasal saline solution (Placebo). Nasal spray, nasal route, vial 20 ml Posology: two sprays, twice a day in each no	n 0.04% (Healsea® Babykids) ostril during a treatment period of 7 to 10 days
Batch number:	Investigator:
Treatment:	Patient:
Expiry Date (mm/yyyy):/	Site:
	com temperature up to 30°C- Keep out of the reach of children
Sp	onsor: Lallemand Pharma AG

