3.8 Investigation Device training/ experience

In real life setting, there is no need for specific training in using **Healsea® Babykids**.

A usability engineering process test according to the standard EN ISO 62366-1:2015 was conducted on Healsea® Babykids with 10 people representatives of the parents/legal guardians of the target

[name] [contact]

population to ensure that the leaflet and the label were well understood, and that the medical device was used correctly to ensure its safe understanding and use.

The analysis of the results demonstrates that:

- The information provided by the user interface is readable and understandable by participants. The information tested was easy to understand, without interpretation.
- The observations made during the simulations of use of the device have confirmed that all safety-related handling steps are properly followed, in accordance with the instructions given in the instruction for use.

Nevertheless, Healsea® Babykids and the comparator will be specially conditioned for this controlled and blinded study. An IFU leaflet is included in each secondary packaging: on one face, the IFU of Healsea® Babykids, on the other face, the IFU of Healsea® Placebo (see 3.9). During the site initiation visit, the investigator will be briefly trained how to use the study devices. After the enrolment, the investigator will instruct each parents/legal guardians on how to use the nasal spray on their child.

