3.9 Reference to the IFU

An IFU leaflet is included in each secondary packaging: on one face, the IFU of Healsea® Babykids, on the other face, the IFU of Healsea® Placebo (See appendix A).

4. Justification for the design of the clinical investigation

The common cold is the most frequent upper respiratory tract infection (URTI), which is the most commonly treated acute problem in primary pediatric care (1). The common cold is an acute viral infection of the upper respiratory tract, involving, to variable degrees, sneezing, nasal congestion and discharge (rhinorrhea), sore throat, cough, low-grade fever, headache, and malaise (2). The common cold is caused by a variety of viruses. Improvements in viral detection techniques during the past two decades, including various viral antigen detection methods and particularly the advent of PCR-based assays, have substantially increased the rates of viral detection in clinical specimens. The relative proportions of different viruses in the cause of the common cold vary depending on several factors, such as age, season, and viral sampling and detection methods. However, rhinoviruses have been consistently found to be the most common cause in all age groups, irrespective of the viral detection techniques used. Yearly, rhinoviruses account for about 30–50% of all respiratory illnesses, but during the autumn peak season these viruses can cause up to 80% of all upper respiratory infections. Coronaviruses and Influenza viruses account for about 10-15% and for 5-15% of acute infectious rhinitis respectively. Other viruses such as Respiratory Syncytial virus, Adenoviruses and Parainfluenza viruses are less involved (2).

Acute viral rhinitis is generally self-limiting. In children where the illness is not self-limiting and extends beyond 7-10 days, many agree that a bacterial infection is likely (2,3). Acute bacterial rhinosinusitis is diagnosed in a child based on several criteria: persistent upper respiratory tract symptoms more than

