7.2 Investigational device and comparator

7.2.1 Description of the exposure to the investigational device

The investigational device will be **Healsea® Babykids.** This is a CE marked Medical Device used for acute rhinitis and administered by spraying 2 puffs in each nostril 2 times per day with a minimum of 7-day-treatment period (14 intakes of the investigational device) up to 10 days (20 intakes of the investigational device). The patient should stop taking the investigational device before D11 only if the guestion 1 "not sick" of the ARSSQ is ticked YES for 2 consecutive days.

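### Every study box carries two spray counts: the labels fix two sprays per nostril, while the enclosed leaflet allows one or two, and nothing says which governs

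*Protocol*

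**What the plan says.** **Labels.** Protocol 3.7.3 prints the same posology on the bottle and on the box: "Posology: two sprays, twice a day in each nostril during a treatment period of 7 to 10 days".

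**Protocol exposure.** Protocol 7.2.1 describes the device as "administered by spraying 2 puffs in each nostril 2 times per day with a minimum of 7-day-treatment period", that is 14 intakes, up to 10 days and 20 intakes. SAP section 3 repeats this.

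**Leaflet.** Protocol 3.9 (and 3.8) states: "An IFU leaflet is included in each secondary packaging". It has one face per product. Under the directions for use in Appendix A, both faces read "One-two sprays twice a day in each nostril for 10 days", followed by "or as recommended by your doctor or pharmacist". Protocol 3.1.1 gives the same one-to-two range in its description of the marketed device.

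**Instruction to parents.** Protocol 3.8 says that "the investigator will instruct each parents/legal guardians on how to use the nasal spray on their child". Protocol 7.4.1 repeats this at dispensing.

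**Compliance.** SAP section 9 computes compliance from bottle weight against a table of theoretical end weights. Protocol section 11 and SAP 7.2 class compliance below 80% or above 120% as a major deviation. SAP section 5 removes major deviations from the Per Protocol Set and keeps the FAS for the primary analysis.

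**The concern.** Two written instructions on the number of sprays go home in the same box, and one permits half of what the other requires. Protocol 7.2.2 says that posology is the same for the two products, but it does not reconcile the leaflet with the label. No section tells the investigator to have parents disregard the leaflet's range.

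A parent could follow the sponsor's own leaflet to the letter and still be recorded as a major deviator. At stake are avoidable under-exposure in the FAS, which would weaken any contrast between the arms, and avoidable loss of children from the supportive Per Protocol analysis. The trial's own packaging would be the cause.

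**Working it through.** **1. Sprays per intake.**

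| Source | Sprays per nostril | Sprays per intake | Over 14 intakes | Over 20 intakes |
|---|---|---|---|---|
| Labels, Protocol 7.2.1, SAP section 3 | 2 | 4 | 56 | 80 |
| Leaflet, lower figure | 1 | 2 | 28 | 40 |
| Leaflet, upper figure | 2 | 4 | 56 | 80 |

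The leaflet's lower figure is exactly half the label figure at every intake.

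**2. What the SAP weights assume.** The initial weight is 32.615 g. The theoretical end weight is 27.55875 g for a stop on D8 morning (14 intakes) and 25.525 g for D11 morning (20 intakes).

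- 14 intakes: 32.615 − 27.55875 = 5.05625 g. 5.05625 / 56 = 0.090 g per spray.
- 20 intakes: 32.615 − 25.525 = 7.090 g. 7.090 / 80 = 0.089 g per spray.

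Protocol 3.7.1 gives 100 ± 20 µl per spray. Taking about 1 g per ml (assumption), 0.09 g lies inside that range. At two sprays per intake the table would imply 5.05625 / 28 = 0.18 g per spray, well outside it. The weights therefore rest on four sprays per intake.

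**3. Score of a child given one spray per nostril throughout, with no missed intakes.** Compliance = 100 × (32.615 − end weight) / (32.615 − theoretical weight). At D11 morning the expected end weight is 32.615 − 7.090/2 = 29.07 g, so compliance = 100 × 3.545 / 7.090 = 50%.

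Pump tolerance does not change the outcome. At 0.08 g per spray the score is 28 × 0.08 / 5.05625 = 44% (14 intakes) or 40 × 0.08 / 7.090 = 45% (20 intakes). At 0.12 g it is 66% or 68%. All are below 80%.

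**4. Partial half-dosing.** If a fraction f of intakes is halved, compliance is 1 − 0.5f, which is below 0.80 only when f > 0.40. That means more than 8 of 20 intakes, or at least 6 of 14. Up to 8 halved intakes of 20 still count as compliant.

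**5. The plan's sample size.** For effect size 0.4, 80% power and two-sided 5%, the normal approximation gives 99 per arm. With 100 per arm, power is 80.7% (80.4% with the t distribution). The stated 100 per arm is reproduced, with almost no slack.

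**6. Illustration of dilution.** Two assumptions are not in the documents: a share q of active-arm children takes half doses, and benefit is proportional to dose. Then the effect size is 0.40 × (1 − q/2).

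| q | Effect size | Power, 100 per arm |
|---|---|---|
| 0 | 0.40 | 81% |
| 10% | 0.38 | 77% |
| 20% | 0.36 | 72% |

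**The case against.** The case on the other side has real substance.

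- **Two sprays satisfies every text.** It is the top of the leaflet's range, so a parent who follows the label and the investigator breaches nothing. The leaflet also defers to medical advice ("or as recommended by your doctor or pharmacist"), and in the trial the investigator gives that advice. This stands as mitigation. It does not make the range a fixed count, and the clause also admits a pharmacist outside the study.
- **The fixed count is in view at each dose.** It is on the bottle, and parents are instructed in person. Consent pages were not available for review, so it would be wrong to infer that parents had only one oral instruction.
- **The range is the device's ordinary direction of use.** Protocol 3.1.1 carries it too. That explains the mismatch without reconciling it.
- **Bottle weighing detects sustained half-dosing.** It does, but only at Visit 2 and only past the threshold in step 4. If the bottle is not returned, Protocol 7.4.1 asks for the number of missed uses, which would not capture halved ones, and SAP section 9 sets compliance to missing.

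A reader might also infer that the leaflet's 10 days conflicts with the label's 7 to 10 days. The documents do not support this. Ten days and 20 intakes is the protocol's own upper limit. The stopping sentence, "The patient should stop taking the investigational device before D11 only if the" child is rated not sick on two consecutive days, restricts early stopping and does not clearly oblige a recovered child to stop. SAP 7.2 lists a deviation only below 14 or above 20 intakes. Nor can a missing stop rule be held against the leaflet alone, since the label has none either.

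**Conclusion.** The conflict on spray count is real, sits in the current text and is unreconciled. Its direct consequence is firm: one spray per nostril is half the assumed exposure and scores about 50% compliance (44% to 68% across the stated pump tolerance, at about 1 g per ml). It therefore meets the listed definition of a major deviation, subject to validation at the data review meeting. The child leaves the Per Protocol Set and stays in the FAS.

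How often this would happen cannot be judged from the documents. The fall from 0.40 to 0.38 or 0.36 depends on an assumed share of 10% or 20% and on assumed dose-proportional benefit. It illustrates scale and is not a forecast of lost power.

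A reader might infer that the comparison is biased towards one arm. The documents do not support that, because both leaflet faces carry the same directions. The risk is dilution and Per Protocol loss. This is an inconsistency in the study materials that should be corrected. It does not invalidate the design or the sample size.

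**What to change.** The sponsor should reconcile Protocol 3.1.1, 3.7.3, 7.2.1 and both faces of the Appendix A leaflet, so that the study box carries a single spray-count instruction. The theoretical weights in SAP section 9 should rest on that same count. If 3.1.1 is meant only to describe the marketed product, it should say so and point to the trial instruction. Which count stands is for the sponsor to decide, and this review takes no position on it.

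The cost is a reprint or overlabel of a leaflet that is already a study-specific two-sided print. Appendix A is part of the protocol, so an amendment signed by the sponsor and the Principal Investigators is also needed (Protocol section 10). Sample size, visit schedule and endpoints are unaffected.
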